Models of Care in the Transition from the Secondary to the Primary Sector among the Frailest Elderly +75; a Randomized Controlled Trial

[name]

Aarhus University Hospital

Randers Regional Hospital

Aarhus University

February 8th, 2019

Models of Care in the Transition from the Secondary to the Primary Sector among the Frailest Elderly +75; a Randomized Controlled Trial

In most Western countries the elderly population increases rapidly. In Denmark, the population of elderly aged 75 years or older may amount to nearly 15 % of the entire population in 2050 compared to 9 % today (2017) (1). A large part of the elderly population is at high risk of hospitalization including more admissions and increased morbidity and mortality (2,3). The number of hospital beds is declining persistently (4), calling for shorter lengths of stay (LOS) (5,6).

Increasingly complex treatments now take place outside hospital. Presently, many Danish regional hospitals establish geriatric wards and other geriatric in-hospital and outpatient services to overcome these challenges. The aim of the present PhD-study is to investigate the effects of different models of transitional care among the frailest elderly patients.

Readmission

Readmitted patients occupy many beds and other hospital resources. Patients are at a risk of high mortality (7) and decline of functional ability (8,9). More than 20 % of Danish medical patients aged 65 years or older become readmitted within 30 days after discharge (10), more frequently in the frail elderly (11). The risk of readmission is particularly high within the first week after discharge, where more than 40% of readmissions happen (12,13). Many reasons and factors for readmissions have been mentioned (11,14-16) such as: former or recent admission, duration of the index hospitalization, degree of comorbidity and low functional ability (11,15). To prevent readmissions it is important to identify the reason for admission and remove it, to ensure that the correct medication is implemented and make sure that adequate social service is provided, to convey unsolved problems to the primary care, ensure continuity during transfer and finally establish sufficient and timely follow-up after discharge (11,14-17).

Identification of patients at risk

Many factors leading to readmission and other adverse events are related to frailty (11,15,18). Prevention of adverse events has traditionally relied on clinicians' and caregivers' ability to anticipate the needs and requirements after discharge. Comprehensive Geriatric Assessment (CGA) is considered as the gold standard to detect frailty (19). To make this easier tools to determine frailty have been developed. In the present study the Multidimensional Prognostic Index (MPI; see Appendix 1A and 1B (slightly adjusted Danish version)) has been chosen to determine the level of frailty. MPI is fully applicable in the everyday clinical work and supplies useful information to clinicians, it is validated in a Danish context, predicts readmission and death (20), and is well-suited to assess the degree of frailty (18,21).

Usual care

Present usual care in Denmark with regard to discharge and transfer, consists of discharge planning. It relies largely on the GP's follow-up visits (see Appendix 2). This approach reduces readmission (22), but the use is limited due to poor implementation, lack of referral, and missing follow-up despite referral (23,24). Only a minor fraction of the frail receives a follow-up visit within the first week after discharge. The GP-based intervention is presently subject to discussion (23,24). Urgent or hospital-at-home-like treatment is needed to avoid readmission. This requires of a well-informed round the clock service. The urgency of follow-up of the frail elderly does not fit into the scheme-based workday of the GP and the on-call GP system. In some districts, additional specialized geriatric wards and outgoing teams exist, but the capacity and contents of these units are limited and vary. Community nurses might after some reorganization hold an untapped potential to improve transition.

Counteractions to readmission

Even though all possible precautions are made before discharge, readmissions still occur. They are often preceded by a series of events stressing the need for multifaceted care and intersectoral efforts in relation to discharge. Many approaches are already applied:

- To avoid obvious and predictable events leading to readmission, comprehensive discharge planning has been introduced in many different countries, probably reducing readmission and LOS without increasing mortality (25,26).
- In a Danish context discharge follow-up is largely based on GP-conducted visits within one week after discharge and offered to a fraction of the elderly.
- Multiple discharge support arrangements have been tested ranging from isolated follow-up telephone calls by a hospital nurse to highly specialized multidisciplinary geriatric teams doing home visits. Early follow-up visits by community nurses have been tested showing possible effect on mortality but not on readmissions (27). Another recent randomized clinical trial (RCT) reports considerable positive effect on readmission, LOS and direct discharge from the ED (12), while a second RCT performed in the same population shows a reduction of

mortality among patients living in their own homes (7). The study shows considerable effect of early team-based home visits applied on selected elderly at high risk of readmission (12).

- Comprehensive Geriatric Assessment (CGA) provides an individualized, multidisciplinary and intersectoral approach when applied by geriatricians in inpatient geriatric wards and in Emergency Departments (ED) and outpatient clinics, in order to improve outcomes of hospitalization. The effects of CGA on readmission, length of stay (LOS) or mortality has yet not been well-proven. It reduces medication and increases the probability of discharge at home (25,28). The effect of CGA combined with an early geriatric home visit has resulted in a significant reduction of the readmission rate within 30 days when compared to the GP-conducted follow-up visits after a week (12).

Outcome measures

According to the various interventions stated above, the outcomes of relevance are readmissions (8-12,15,17,22,24-26,28-44), mortality (7,8,10,12,25,27,28,30-32,38-41,44), length of stay (LOS) (12,25,28,29,32,38,41,45), direct discharge from the ED (12,29), time at home (10,25,27,34), duration of readmission (10,25,34) and physical functional status (8,25,27,28,30,31,34,40,43-45). A successful intervention may be reflected in a shorter LOS, lower risk of readmissions, longer time at home, maintained functional status and a shorter duration of readmission. We suggest that a significant and effective intervention under the best circumstances is reflected in these outcomes. Readmissions are usually considered as such, when the admission occurs within 4 hours after and before 30 days after discharge. Among the frail, in-hospital and post-discharge mortality is high, needing frequent assessment. As shown by Pedersen et al. (7), mortality differs with regard to type of dwelling. Former studies have shown a significant and remarkable reduction of LOS (reduction from median 3 days to median 2 days) and an increase from 49 % to 56 % of patients discharged directly from the ED due to the possibility of early follow up by a geriatric team (12). Functional status is of relevance, especially combined with mortality data, since a better survival of the frailest may be combined with a worsened functional status in the total group. Patient Related Outcome Measures (PROMs) will be assessed and added as secondary outcomes during the project. Patient satisfaction and costs are other relevant outcome measures with regards to the triple aim principle, but will not be included in the present Ph.D. project.

Conclusion

While some previously tested interventions, including CGA and discharge support arrangements, have been futile (25,31,46), we believe that multidisciplinary, tailored interventions used in selected high-risk groups throughout hospitalization and discharge are effective (8,12,29,34,44). Most former studies regarding early follow-up visits and CGA are made in geriatric settings, somewhat distanced to usual care and municipality services. Many previous trials have included patients without looking in particular for frail high-risk patients, thereby probably underestimating the effects of the intervention. It is not known if an early visit by a community nurse would have the same effect as an early geriatric home visit. Selection of elderly patients who will benefit from home visits by a geriatric team after discharge compared with a community nurse visit or usual care may be useful. MPI has been able to predict mortality, LOS (47), and readmissions (48), but has not previously been tested as a selection tool to distinguish between different follow-up methods. It has been suggested that the major effect from early follow-up is more or less independent of the type of follow-up, but is caused by the early visit itself. The type of dwelling may influence the effect of an early visit, since the care setup in some nursing homes may resemble that of a hospital. The level of frailty may influence the effectiveness and efficacy of the different follow-up schemes. Some patients may be chronically frail and their frailty may already have been handled prior to admission, in a way that dilutes the effect of early follow-up visits. The length of stay and other secondary endpoints may rely largely on the planned follow-up approach. The level of frailty predicts the risk of readmission and mortality and can therefore be used as a major indicator when clinicians have to choose between different follow-up approaches.

Objectives

The aim of this study is to investigate the effects of two interventions using CGA and early post-discharge follow-up visits in a population of frail 75+ year-olds compared to usual care. The vision is to find feasible and durable approaches that can improve patient outcome in the transition from hospital to primary health care. We are aiming to identify subjects who will profit the most from each approach.

All frail patients admitted to the ED and the Department of Geriatrics are randomized 1:1 to one of two different follow-up efforts prior to CGA performed during hospitalization. Thereby the intervention is randomly split into two groups:

- An intervention (I) consisting of CGA during hospitalization and early post-discharge follow-up care by a community nurse and a GP
- An intervention (II) consisting of CGA during hospitalization and early post-discharge follow-up care, including continued CGA and tailored follow-up care, by a geriatric team

The intervention cohort will be compared to a control cohort consisting of similar frail elderly who receive usual care without involvement of geriatric care during hospitalization and after discharge.

Hypotheses

- The geriatric team follow-up is as effective as a community nurse and GP follow-up measured by readmission, mortality, LOS, direct discharge from ED and physical functional recovery
- The effects of three transitional follow-up approaches (community nurse and GP; multidisciplinary geriatric team; usual care) are similar measured in terms of readmission, time at home, duration of readmission, LOS, direct discharge from ED, mortality and PROMs
- When stratified into subgroups with regards to level of frailty (moderate and severe) and type of dwelling, the geriatric team follow up is as good as community nurse and GP follow-up measured by readmission, mortality, LOS, direct discharge from ED and physical functional recovery

Methods

Design

The first study is conducted as a randomized controlled trial (RCT) using two different degrees of intervention. The second study is a cohort study where the two groups in the RCT are compared to an unexposed control group. The third study is sub-group analyses of the RCT data according to frailty status and type of dwelling.

Study population

The population allocated to intervention comprises geriatric patients acutely admitted to the ED, Aarhus University Hospital (AUH) or transferred to one of the two geriatric wards at AUH. Subjects are included immediately on the day of admission at the ED, AUH and the Department of Geriatrics (wards 1 and 2), AUH, as shown in Fig. 1. Patients admitted to the ED at night and promptly discharged before enrollment to the intervention cohort can be performed the following day are not included. Likewise, patients to the control group are included immediately on the day of admission at the ED, Randers Regional Hospital (RRH), and at the medical wards 1, 2, 3 and 4, RRH. Patients transferred to other departments are excluded. Patients can only be included once. Enrollment and randomization to the intervention group are performed by therapists working in the ED or the geriatric wards. Enrollment to the control group is done by a Research Assistant. In the control group frailty screening is done by the PhD-student using a frailty screening tool based exclusively on data collected through medical records. The frailty screening tool will be validated by crosschecks performed by a blinded project Research Assistant. The results of the validation study will be analyzed and published during 2019.

Inclusion criteria:

- Aged 75 years or older
- Living within the municipality of Aarhus (except for the control group, see below)
- MPI-score = 2 (moderate frailty) or MPI score = 3 (severe frailty)

Exclusion criteria:

- Included in any other kind of follow-up schemes
- Declared terminally ill or undergoing palliative care at admission
- Admitted from one specific temporary nursing home with geriatric medical assistance (Vikærgården)
- Discharge or transfer to another department, including hospice
- MPI-score = 1 (low frailty)
- Discharged to one specific temporary nursing home with geriatric medical assistance (Vikærgården)
- The patient does not want a visit after discharge

Inclusion- and exclusion criteria to the control group are the same as for the two intervention groups, except that subjects eligible for the control group are living within the four municipalities of RRH: Randers, Favrskov, Norddjurs and Syddjurs.

Randomization

As shown in Fig. 2, all intervention group patients are allocated at the time of randomization on the day of admission to receive either early visit from the community nurse (I) or the multidisciplinary geriatric team (II). The randomization is stratified with regard to dwelling (living alone; cohabiting; nursing home) and number of drugs prescribed prior to

admission (0-3, 4-7, 8 or more drugs), and conducted using the randomization function in REDCap (49). Randomization is open throughout the whole admission with the purpose to enable early discharge planning.

Intervention I and II

Both intervention groups are assessed according to CGA, either by the geriatrician and the physiotherapist/geriatric nurse in the ED, or by a multidisciplinary team comprised of geriatricians, specialized nurses, physiotherapists and occupational therapists during hospitalization in the geriatric wards.

- Intervention (I): comprises early follow-up visit from the community nurse within 24 hours after discharge, and the possibility of consulting a nutritionist, thus supplementing usual care services including the possibility of consulting the patients' GP. Responsibility of treatment including implementation of suggested initiatives and any further assessment is handed over to the GP at discharge.
- Intervention (II): CGA is continued during early follow-up by the geriatric team. On weekdays visits are scheduled within 24 hours after discharge. For patients discharged during weekends or holidays, supporting telephone calls are provided by the geriatric team. If needed, the geriatric team nurse visits the patient. The concept of CGA in this stage does not differ from the above-mentioned. There are no standardized demands, but a part of the intervention can be to perform hospital services at home and continued treatment and diagnostics after discharge. The possible services provided by the geriatric team are further described in the geriatric team course description. The responsibility of treatment rests with the geriatric team until dispatch of the discharge summary. Patients then return to usual care. The geriatric team follow-up is planned to last a maximum of 7 days, yet allowing extension for as long as there is a need for services performed exclusively by the geriatric team as described in the geriatric team course description.

Control group

The patients in the control group are discharged to usual care and do not receive early follow-up visits. Usual care features municipality services and optionally a GP home visit (see Appendix 2). Eligible control patients are consecutively included by a Research Assistant. The estimated level of frailty will be assessed by the PhD-student based on a MPI-screening tool fitted to be performed using only medical record data. This fitted tool will be tested and validated prior to the inclusion of the control group. Clinicians will be blinded to the result of the MPI-screening of the control subjects to ensure that discharge is performed in accordance with usual care.

Outcomes

The primary outcome is readmission within 30 days after discharge. Secondary outcomes are:

- Mortality 30 days after discharge and 90 days after admission
- Length of stay during primary admission and total length of stay including following readmissions
- Direct discharge from the Emergency Department
- Time at home before readmission
- Duration of readmission
- Physical functional status 30 days after discharge (Functional Recovery Score)
- Patient Related Outcome Measures as defined by a focus group of included patients and/or their relatives

Statistical analyses

Data are registered in REDCap and exported to STATA version 15 for the statistical analyses. Statistical significant results are defined as a p-value of 5% or less. The two intervention groups and the control group will be compared with regard to baseline measures. If needed, statistical corrections for demographical differences and level of frailty will be made. The use of services and other contents of follow-up will be assessed and compared if possible. Baseline data collected for the entire study population before discharge are: age, gender, date of admission, co-habitation status, number of drugs, and level of frailty measured by MPI including functional status by means of Functional Recovery Score (FRS) at discharge. Follow-up data for the control group will be collected on type of planned care after discharge. Follow-up data for the entire study population will be collected on: department of discharge, date of discharge, primary diagnosis at discharge, dwelling after discharge, readmission date, and death date. For the intervention cohort additional data are collected: date of follow-up, provided services after discharge, number and date of visits (team, GP, nurse) after discharge, phone-calls to the geriatric team or GP, nutritionist consultations, FRS after 30 days, date of dispatch of discharge summary. Additional data will be collected by review of the electronic patient records.

Outcomes

A hazard ratio (HR) for readmissions will be calculated using a Cox regression model with death as a 'competing risk' factor. The HRs of readmission with 95% confidence intervals (95% CI) for interventions I and II will be compared individually and to the control group. The interventions will be tested in subgroup analyzes based on: patients discharged directly from the ED, type of dwelling and level of frailty. Median LOS, time at home before readmission and duration of readmission will be calculated and compared using the Wilcoxon rank-sum test. The mortality hazard ratio will be calculated also using the Cox regression model. The change in functional status at discharge and 30 days after discharge will be compared in a linear regression model. Data will be analyzed in accordance with intention-to-treat and per-protocol analysis.

Sample size

Power analysis is based on a pilot study performed from June to December 2017 using the method stated above, and earlier studies by Pedersen et al.(7,12), where patients selected by diagnoses associated with readmission were randomized to early geriatric follow-up visits or usual care. Readmissions were reduced from 23% to 12%. Data collected during the pilot study showed 13.7% readmissions in the Intervention group I compared to 8% readmissions in the Intervention group II. Based on the pilot study data, allowing a 5% drop-out rate and a 30-day mortality rate of 10%, the number of patients in each trial arm should be 758 in order to achieve a power of 90% and a level of significance of 5%. Data collected during the same pilot study showed a 90-day mortality rate of 20.6% in Intervention group I compared to 15.6 % in Intervention group II. To achieve a power of 80% and a level of significance of 5% with regards to mortality, the sample size of each arm should be 1,019, including a 5% drop-out rate.

Perspectives

This study may uncover a need for specialized and early efforts to support transfer of the frail elderly. We may find that some of the frail elderly are poorly supported by the present follow-up procedures, suggesting that comprehensive geriatric assessment and early follow-up intervention by a community nurse and a geriatric team should gain further currency in the future. This study may contribute to dimension health care services in the future. We hope to clarify the possible need for geriatric services outside university hospitals. The results are directly transferable to Danish regional hospitals and may be of importance in other Western countries.

Ethics

The study has been approved as a quality development project by the Regional Research Ethics Committee, Central Denmark Region (journal no. 197/2017), thereby no patient consent form is needed, and further referral to the committee not required. No patient will receive less than usual care, no extra treatment or examination will be applied, and no patient will be exposed to any additional risk because of the project. Participants may decline parts of or the entire intervention, including usual care, at any time. The project, which is a part of the national rate adjustment pool-project "Early post-discharge follow-up of the frail elderly – a intersectoral effort" in the Central Denmark Region, is approved by the Danish Data Protection Agency (journal no. 2012-58-006).

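### The plan wants to find who benefits most from each follow-up model, but it plans only subgroup tests, which cannot show that effects differ or that the models are equally good

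*Protocol*

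**What the plan says.** In both documents, the Objectives section sets a treatment-selection aim: "We are aiming to identify subjects who will profit the most from each approach". The third hypothesis takes frailty level (moderate, severe) and type of dwelling and states that, within these subgroups, "the geriatric team follow up is as good as community nurse and GP follow-up measured by readmission", and likewise for mortality, LOS, direct discharge from the ED and functional recovery.

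The outcome paragraph under Statistical analyses says the interventions will be tested in subgroups defined by direct discharge from the ED, dwelling and frailty. No interaction term is mentioned. Dwelling has three levels: "The randomization is stratified with regard to dwelling (living alone; cohabiting; nursing home". The only decision rule is: "Statistical significant results are defined as a p-value of 5% or less". A 95% CI is promised for the readmission hazard ratio. None is stated for mortality (Cox hazard ratio), LOS (rank-sum test) or functional change (linear regression).

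The first two hypotheses are also worded as equality: "The geriatric team follow-up is as effective as a community nurse and GP follow-up measured by readmission" and "The effects of three transitional follow-up approaches (community nurse and GP; multidisciplinary geriatric team; usual care) are similar". None of the three is called a null, and no alternative or margin is given. The Sample size section is built on pilot differences between the two randomised arms: 13.7% vs 8% for readmission and 20.6% vs 15.6% for 90-day mortality.

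**The concern.** The aim asks whether the difference between the geriatric team and nurse/GP follow-up varies with frailty or dwelling. A p-value computed within each subgroup answers something else: whether a difference is detectable there, which depends heavily on subgroup size. One significant and one non-significant subgroup can easily arise when the true effect is identical in both.

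The equality wording adds a second risk. A subgroup with few events will often give p>0.05, and the third hypothesis could then be read as confirmed where the data say least. Services could be assigned to, or withheld from, frailty or dwelling groups on that basis.

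Direct discharge from the ED is a further problem as a subgroup factor. It happens after randomisation, allocation is open so that discharge can be planned early, and it is itself a listed secondary outcome. The arms may therefore differ in who enters that subgroup.

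**Working it through.** **Inputs.** From Sample size: readmission 13.7% vs 8%, 90% power; mortality 20.6% vs 15.6%, 80% power; 5% significance; 5% drop-out; 10% 30-day mortality for the readmission calculation. Subgroup shares and the event rate in a no-effect subgroup are not given and are assumed below.

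**1. The plan's own sizes.** Two-proportion formula, two-sided 5%, with d the difference and p̄ the mean rate: n = [1.960√(2p̄(1−p̄)) + z_power√(p1(1−p1)+p2(1−p2))]² / d². The continuity correction is n_c = (n/4)[1+√(1+4/(nd))]².
- Readmission: n = 623.6, n_c = 658.2, so 659; 659 × 1.15 = 757.85, so 758.
- Mortality: n = 929.6, n_c = 969.2, so 970; 970 × 1.05 = 1,018.5, so 1,019.

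Both match exactly. One-sided versions do not, so the sizing is for a two-sided difference.

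**2. Evaluable patients per arm.** The documents do not say which size is adopted, so three values are carried:
- 758 × 0.95 × 0.90 = 648 (drop-outs and deaths removed)
- 758 × 0.95 = 720 (deaths kept, as the competing-risk analysis does)
- 1,019 × 0.95 = 968

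**3. Missing the full planned effect within a subgroup.** Power is Φ[(d − 1.960·se0)/se1], where se0 = √(2p̄(1−p̄)/n) and se1 = √((p1(1−p1)+p2(1−p2))/n). For half of 648, n = 324, se0 = 0.02444 and se1 = 0.02433. Then (0.057 − 1.960 × 0.02444)/0.02433 = 0.374, power is 0.646 and the miss rate is 0.354.

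| Assumed share of each arm | 648 | 720 | 968 |
|---|---|---|---|
| 50% | 35% | 31% | 18% |
| One third (equal dwelling groups) | 52% | 48% | 36% |
| 25% | 62% | 59% | 48% |

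For comparison, the whole-trial miss rates are 9%, 6% and 2%.

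**4. Discordant p-values with no true interaction.** Take two equal halves, each with the full planned effect. The chance that exactly one is significant is 2 × miss × (1 − miss):
- 648: 2 × 0.354 × 0.646 = 46%
- 720: 2 × 0.308 × 0.692 = 43%
- 968: 2 × 0.185 × 0.815 = 30%

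**5. Power of an interaction test.** Assume 13.7% vs 8% in a subgroup with share s and no effect elsewhere, where the common rate is r. On the risk-difference scale, se² = [0.137×0.863 + 0.08×0.92]/(ns) + 2r(1−r)/(n(1−s)), and power is about Φ(0.057/se − 1.960). For n = 648, s = 50%, r = 13.7%: se² = 0.1918/324 + 0.2365/324 = 0.001322, se = 0.0364, 0.057/se = 1.568 and power is 35%.

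| r | s | 648 | 720 | 968 |
|---|---|---|---|---|
| 13.7% | 25% | 29% | 31% | 40% |
| 13.7% | 50% | 35% | 38% | 48% |
| 8% | 25% | 32% | 34% | 44% |
| 8% | 50% | 42% | 46% | 58% |

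These figures are for a two-group contrast.

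**6. Whole-trial non-significance, for the labelling point.** By the step 3 formula, a true 3-point readmission difference (13.7% vs 10.7%, an illustrative value) gives p>0.05 in 62%, 59% and 48% of trials at 648, 720 and 968. The plan's own mortality difference gives p>0.05 in 31% at 720 and 18% at 968.

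**The case against.** A reader might infer from the equality wording that this is an equivalence or non-inferiority trial with its margin left out, and so with the wrong sample size. The documents do not support that. Both sizes reproduce exactly as tests of a difference. The authors write "we believe that multidisciplinary, tailored interventions used in selected high-risk groups throughout hospitalization and discharge are effective" and "It is not known if an early visit by a community nurse would have the same effect as an early geriatric home visit", and calling usual care similar to both interventions makes sense only as a null. The three statements are most likely nulls without a label, and on that reading hypotheses, tests and sizing fit together.

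A reader might also infer that the investigators intend to report p>0.05 as equality. Neither document says so. The promised CI for the readmission hazard ratio is a real safeguard for the primary outcome, at the full planned effect the whole-trial test rarely fails, and the linear regression for function will yield an estimate. What stands of the labelling issue is therefore a clarification.

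Against the subgroup point, it can be said that interaction power is low, that the shares are assumed, and that the planned model uses hazard ratios while the power was computed on risk differences. All three are true. On an approximate log hazard ratio scale the range is similar, about 28-57%, although the ordering by no-effect rate reverses. Low power limits what can be concluded; it does not make separate p-values a valid substitute.

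**Conclusion.** The concern holds for the subgroup analysis. The stated aim needs a test of whether the effect differs between subgroups, and none is planned. The within-subgroup tests would miss the full planned readmission effect in 18-62% of trials, across subgroup shares of 50% down to 25% and 648 to 968 evaluable per arm. With identical effects in two halves, 30-46% of trials would still show exactly one significant half. These ranges rest on the plan's rates, assumed shares and a normal approximation for proportions. The logical point depends on none of them.

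The equality wording of the three hypotheses is a secondary matter of labelling. It is not evidence of a wrong design or a wrong sample size. The change should be made before analysis.

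**What to change.** In both documents:

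1. For the third hypothesis and the treatment-selection aim, add an arm-by-frailty and an arm-by-dwelling interaction term to the readmission model, with dwelling as classified at randomisation. Report each subgroup's estimate with a 95% CI. Base any statement about who benefits most on the interaction, and report a non-significant interaction as not shown.
2. Do not use direct discharge from the ED for this claim.
3. Label the three hypotheses as nulls with two-sided alternatives, for all outcomes each one names and not readmission alone. Keep the usual-care comparison as an adjusted, non-randomised one.
4. Report p>0.05 as no difference shown, with an effect estimate and 95% CI for every named outcome, and not as equality or similarity.

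Cost: no extra patients or data; 758 and 1,019 stand. The price is weaker claims after null results and an interaction test with about 29-58% power under the assumptions above. The three-level dwelling test needs two degrees of freedom, which those figures do not cover.

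### The I v II length-of-stay test pools ED and geriatric-ward enrolees; stratifying it by place of enrolment would be a cheap, optional gain in precision whose size the documents do not fix

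*Protocol*

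**What the plan says.** The Protocol and the earlier Combined protocol and SAP agree on every item below.

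- **Enrolment** (Study population): "Subjects are included immediately on the day of admission at the ED, AUH and the Department of Geriatrics (wards 1 and 2), AUH". The split between the ED and the wards is not given.
- **Randomisation** (Randomization): "The randomization is stratified with regard to dwelling (living alone; cohabiting; nursing home) and number of drugs". Place of enrolment is not a stratum.
- **LOS analysis** (Statistical analyses, Outcomes): "Median LOS, time at home before readmission and duration of readmission will be calculated and compared using the Wilcoxon rank-sum test". No stratification or covariate is mentioned.
- **Adjustment** (Statistical analyses): "If needed, statistical corrections for demographical differences and level of frailty will be made". Place of enrolment is not named here, nor in the list of baseline data.
- **Subgroups** (Statistical analyses, Outcomes): "patients discharged directly from the ED, type of dwelling and level of frailty". The first of these is known only after randomisation.
- **Cited effects** (Outcome measures): earlier work on geriatric-team follow-up is reported to have cut median LOS from 3 to 2 days, with "an increase from 49 % to 56 % of patients discharged directly from the ED".

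LOS is a secondary outcome and is named in all three hypotheses. The Sample size section covers readmission and mortality only.

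**The concern.** A patient enrolled in the ED may go home from there. A patient enrolled on a geriatric ward has already been moved to inpatient care and cannot. In the cited earlier study about half of patients left directly from the ED, so it is reasonable to expect different LOS distributions by place of enrolment. A pooled rank-sum test ranks both kinds of stay together, and any difference between places becomes noise in the comparison of I with II. A test stratified by place compares arms only within each place and removes that noise.

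What is at stake is sensitivity. The randomised contrast may well be modest, because both arms receive in-hospital CGA and an early visit, and the Protocol's own Conclusion section allows that the benefit may come mainly from the visit being early. The hypotheses are also worded as the team being as effective as nurse and GP follow-up, with no LOS margin. A non-significant LOS result could therefore be read as support, and avoidable noise makes such a result more likely.

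**Working it through.** **The plan's own figures.** No power or sample size is stated for LOS, so there is no LOS figure to reproduce. The arm size used below does reproduce. For readmission of 13.7% v 8%, two-sided 5% and 90% power, the two-proportion formula gives

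n = [1.96·√(2·0.1085·0.8915) + 1.2816·√(0.137·0.863 + 0.08·0.92)]² / 0.057² ≈ 624.

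The continuity correction, (n/4)·[1 + √(1 + 4/(n·0.057))]², raises this to 659, and 659 × 1.15 = 758 per arm as stated. After 5% drop-out, 758 × 0.95 = 720.

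**Tests compared.** In stratum k, with n_k patients of whom m_k are in arm II, let W_k be the sum of arm II ranks.

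- Pooled: Z = [W − m(n+1)/2] / √Var(W), with all patients as one stratum.
- Stratified (van Elteren): Z = Σ{[W_k − m_k(n_k+1)/2]/(n_k+1)} / √Σ{Var(W_k)/(n_k+1)²}, with ED and ward as strata.

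Both use the tie-corrected variance and reject when |Z| > 1.96.

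**Assumed inputs (none is in the documents).** LOS is lognormal, rounded up to whole days. The arm effect multiplies LOS by a ratio, so 0.85 is a 15% shorter stay. Each setting has 3,000 simulated trials, giving a Monte Carlo standard error of at most √(0.25/3000) = 0.9 points.

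*Setting A: each place has its own median, log-SD 0.9, half enrolled in the ED, 758 per arm. Power, pooled v stratified:*

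| Median ED / ward (days) | Ratio 0.90 | Ratio 0.85 | Ratio 0.67 (3 to 2 days) |
|---|---|---|---|
| 3 / 3 | 58% v 58% | 92% v 92% | 100% v 100% |
| 2 / 4 | 52% v 59% | 89% v 93% | 100% v 100% |
| 1.5 / 6 | 39% v 57% | 74% v 91% | 100% v 100% |
| 1 / 8 (extreme) | 26% v 56% | 54% v 90% | 99.9% v 100% |

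With 720 per arm, medians 1.5 / 6 and 1,500 trials, power is 72% v 90% at ratio 0.85 and 59% v 81% at ratio 0.87.

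*Setting B: 49% of ED enrolees leave directly (median 1 day, log-SD 0.6). The other ED enrolees and all ward enrolees have a median of 6 days (log-SD 0.8). 758 per arm. Power, pooled v stratified:*

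| ED share | Ratio 0.85 | Direct discharge 49% to 56%, no other effect |
|---|---|---|
| 50% | 80% v 89% | 20% v 20% |
| 75% | 71% v 80% | 38% v 38% |
| 90% | 70% v 75% | 51% v 52% |

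**Type I error.** With no effect (medians 1.5 / 6, half from the ED, 720 per arm), the rejection rate was 5.3% pooled and 5.6% stratified.

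**Reading the tables.** At ratio 0.85 the gain is nil when places do not differ and about 4 points at 2 v 4 days. It is about 5 to 9 points in setting B and about 17 to 19 points at 1.5 v 6 days. It reaches 36 points only in the 8-fold extreme. At the cited LOS effect, or for the cited direct-discharge shift alone, it is essentially nil.

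**The case against.** The strongest case against is that nothing here is an error. The pooled test holds its level, randomisation balances place of enrolment on average, LOS is one of several secondary outcomes, and no power is claimed for it. All of that stands.

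A reader might infer that the plan throws away much of its power for LOS. The documents do not support that. The large gains need a four-fold or greater ED/ward gap in median stay together with a small I v II effect, and neither figure is given. The cited 49% direct discharge points towards the smaller gains: if about half of ED enrolees go home directly, the rest stay on, and their stays overlap those of ward enrolees, as in setting B.

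At the only LOS effect cited, stratification makes no difference. This disposes of less than it seems to, because that effect came from team follow-up in earlier studies and not from the present contrast of two early-visit arms. A smaller effect is possible, and the gain would arise there.

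It could also be said that the direct-discharge subgroup already covers the distinction. It does not: leaving directly from the ED is itself an outcome, open to influence by an allocation that is known throughout the admission.

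A reader might extend the point to the Cox models for readmission and mortality. No gain was calculated for them, and the extension is not made here.

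**Conclusion.** The point holds as a cheap, optional gain in precision for a secondary outcome. Place of enrolment is fixed before allocation, plausibly predicts LOS, and is absent from both the randomisation strata and the LOS test. The planned test is valid but may be less sensitive than it need be. In plausible settings the gain runs from about zero to about 20 percentage points, and where it falls depends on the ED/ward split, LOS by place, LOS spread and the true I v II effect, none of which the documents give. Across the settings shown, the stratified test had power about equal to or higher than the pooled test. The primary readmission analysis is not affected.

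**What to change.** Record place of enrolment (ED or geriatric ward) as a field at randomisation. State in the statistical section, before outcomes are compared, that LOS in I v II will be analysed with a rank-sum test stratified by that place (van Elteren), or with a proportional-odds model containing that term. Use the place at randomisation. Department of discharge, which is already collected, must not stand in for it, because allocation can influence it.

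The cost is a sentence or two of analysis text and one extra field. The enrolling therapists work in the ED or on the wards, so the value is known at enrolment. For patients already enrolled it would have to be recovered from the record, since it is not among the listed baseline data.
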